6.0 Study Drug Duration

The overall treatment duration will be summarized separately for Run-in-Period and Treatment Period. Duration of treatment is defined for each subject as (last dose date first dose date + 1). Duration of treatment will be summarized using the number of subjects treated, mean, standard deviation, median, minimum and maximum.

- 1. Summary of Duration of treatment in Run-in Period using FAS and SAS-CREON-ABT population separately. In addition, the number and percentage of subjects in each treatment duration interval 1 to <8 days of treatment, 8 to <15 days of treatment and >=15 days treatment will be summarized.
- 2. Summary of Duration of treatment in the Treatment Period using FAS population. In addition, the number and percentage of subjects in each treatment duration

interval (, 1 to \leq 8 days, 8 to \leq 15 days, 15 to \leq 29 days, 29 to \leq 85 days, \geq 85 days) will be summarized.

7.0 Demographics, Baseline Characteristics, Medical History, and Prior/Concomitant Medications

[figure not shown]
Demographics, Baseline or disease characteristics, medical history, and prior and concomitant medications will be summarized for the FAS population. Categorical variables will be summarized with the number and percentage of subjects; percentages will be calculated based on the number of non-missing observations. Continuous variables will be summarized with descriptive statistics (number of non-missing observations, mean and standard deviation, median, minimum and maximum).

7.1 Demographics and Baseline Characteristics

Continuous demographic variables include age, weight, height, body mass index (BMI), and TSS both at the start of the Run-in Period and at Baseline (Day 1), and prior Creon total daily dose. Categorical demographic variables include sex (male, female), ethnicity (Hispanic or Latino, Not Hispanic or Latino), race (White, Black, American Indian/Alaska Native, native Hawaiian or Other Pacific Islander, Asian, Multi, or Other), study population (CF only, CP only, or CF and CP), weight (< 60 or ≥ 60 kg), BMI (< 25 or ≥ 25 kg/m²), tobacco user (current, former, never, unknown), and alcohol user (current, former, never, unknown).

7.2 Medical History

Medical history data will be coded using the Medical Dictionary for Regulatory Activities (MedDRA). The actual version of the MedDRA coding dictionary will be noted in the statistical tables and clinical study report. The number and percentage of subjects in each medical history category (by MedDRA system organ class and preferred term) will be summarized. The system organ class (SOC) will be presented in alphabetical order, and the preferred terms will be presented in alphabetical order within each SOC. Subjects

reporting more than one condition/diagnosis will be counted only once in each row (SOC or preferred term).

7.3 Prior and Concomitant Medications

Prior and concomitant medications will be summarized by generic name. The number and percentage of medications will be summarized per subject for both prior and concomitant medications.

[figure not shown]
A prior medication and procedure are defined as any medication and procedure performed prior to the date of the first dose of CREON-ABT. This includes medications and procedures with a start date before the first dose of CREON-ABT. In cases where incomplete or missing medication and procedure dates are collected, a conservative approach will be taken and it will be counted as a prior medication and procedure.

A concomitant medication for CREON-ABT is defined as any medication that started prior to the date of the first dose of CREON-ABT and continued to be taken after the first dose of CREON-ABT or any medication that started on or after the date of the first dose of CREON-ABT, but not after the date of the last dose of CREON-ABT.

A concomitant medication for CREON-SPL is defined as any medication that started prior to the date of the first dose of CREON-SPL and continued to be taken after the first dose of CREON-SPL or any medication that started on or after the date of the first dose of CREON-SPL, but not after the date of the last dose of CREON-SPL.

In the situation where an incomplete or missing medication date is collected, a conservative approach will be taken and it will be counted as a concomitant medication unless there is evidence that the medication was not taken during the study drug treatment (e.g., an end date before the first dose of study drug (CREON-ABT or CREON-SPL, where applicable).

A concomitant procedure for CREON-ABT is defined as any procedure that started prior to the date of the first dose of CREON-ABT and continued after the first dose of CREON-

ABT or any procedure that started on or after the date of the first dose of CREON-ABT, but not after the date of the last dose of CREON-ABT.

A concomitant procedure for CREON-SPL is defined as any procedure that started prior to the date of the first dose of CREON-SPL and continued after the first dose of CREON-SPL or any procedure that started on or after the date of the first dose of CREON-SPL, but not after the date of the last dose of CREON-SPL.

In the situation where an incomplete or missing procedure date is collected, a conservative approach will be taken and it will be counted as a concomitant procedure unless there is evidence that the procedure was performed before the study drug treatment (e.g., an end date before the first dose of study drug (CREON-ABT or CREON-SPL, where applicable).

Note that a medication or a procedure can be considered both a prior and concomitant medication or procedure if it started prior to the first dose of study drug (CREON-ABT or CREON-SPL, where applicable) and continued after the first dose of study drug.

[figure not shown]
Prior procedures and concomitant procedures will be listed by subject numbers.

8.0 Handling of Potential Intercurrent Events for the Primary and Key Secondary endpoints

The pharmacodynamic endpoints (TSS, ASDS and BMSS) will be analyzed based on the PP population and the following potential intercurrent events will be addressed:

- Subjects who did not receive any dose of study drug **CREON-SPL** will be excluded from the PP population.
- Subjects who did not have Baseline (Day 1) PEI-Q score data or did not have any post-Baseline PEI-Q score data will be excluded from the PP population.

Subjects who have missing PEI-Q data for a particular visit (besides Day 1) will be excluded from the analysis of that visit.

9.0 Pharmacodynamic Endpoint Analyses

9.1 General Considerations

All pharmacodynamic analyses will be conducted in the PP population.

This is a descriptive and exploratory study. No formal statistical hypothesis is being tested.

All the analyses will be performed after all ongoing subjects have completed the Treatment Period and the database has been locked. This will be the final analysis for the pharmacodynamic endpoints.

"Baseline" refers to the last non-missing observation before the first administration of CREON-SPL, unless otherwise specified in the individual analysis section.

9.2 Pancreatic Exocrine Insufficiency Questionnaire (PEI-Q) Domain Scores

The Pancreatic Exocrine Insufficiency Questionnaire (PEI-Q) is provided in Appendix C. It is comprised of three domains: abdominal symptoms, bowel movements, and impacts. Assessment of EPI symptoms will be done using abdominal symptoms domain, bowel movement symptoms domain, and the Total Symptom Score.

9.2.1 Abdominal Symptoms Domain Score (ASDS)

The Abdominal Symptoms Domain (ASD) consists of 7 questions, each with 5 answer choices. A score of 0 - 4 will be assigned to each answer as specified in the Table 1. The Mean Abdominal Symptoms Domain Score (A) is the average of the total score. The mean score for this domain can range from 0 to 4.

Table 1. PEI-Q Score Assignment

ANSWER	SCORE
NO NOT AT ALL	0
YES, A LITTLE BIT	1
YES, SOME	2
YES, QUITE A BIT	3
YES, A LOT	4

9.2.2 Bowel Movement Symptoms Score (BMSS)

The Bowel Movement Symptoms (BMS) consists of 6 questions, each with 5 answer choices. A score of 0 - 4 will be assigned as specified in the Table 1. The Mean Bowel Movement Symptoms Score (B) is the average of the total score for this domain. The mean score for this domain can range from 0 to 4.

9.2.3 Total Symptom Score (TSS)

The Total Symptom Score will be calculated as the average of the Mean Abdominal Symptoms Domain Score (A) and Mean Bowel Movement Symptoms Score (B). It can range from 0 to 4.

[figure not shown]
9.3 Handling of Missing Data in PEI-Q

The PEI-Q data are designed to be collected when all questions are answered, so there will be no missing data. Subjects who have missing PEI-Q data for a particular visit (besides Day 1) will be excluded from the analysis of that visit.

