7.3 Handling Potential Intercurrent Events for the Study Endpoints

The pharmacodynamic endpoints (TSS, ASDS and BMSS) will be analyzed based on the PP population and the following potential intercurrent events will be addressed:

- Subjects who did not receive any dose of study drug CREON-SPL will be excluded from the PP population.
- Subjects who did not have baseline (Day 1) PEI-Q score data or did not have any post-baseline PEI-Q score data will be excluded from the PP population.

Subjects who have missing PEI-Q data for the visit will be excluded from the analysis of that visit.

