2.4 Sample Size Determination

Approximately 30 subjects will be enrolled at the Run-in-Visit (RIV). The sample size is calculated based on the descriptive statistics for the change in TSS based on PEI-Q. No formal statistical hypothesis testing is planned. Assuming a dropout rate of 20% after the RIV, the number of evaluable subjects will be around 24 for the analysis of pharmacodynamic endpoints.

Based on Johnson CD, et al,¹ the average TSS from PEI-Q was estimated to be 1.4 (SD = 0.7) for CP and CF subjects with EPI symptoms. Assuming the covariance between the TSS at Baseline and post-Baseline after switching to **CREON-SPL** to be 0.365, the SD for the change of the TSS between Baseline and post-Baseline is estimated to be 0.5. A sample size of 24 evaluable subjects will provide a precision of \pm 0.2 in terms of halflength of the 95% confidence interval for the estimate of change in TSS based on PEI-Q.

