4.0 Analysis Populations

The following population sets will be used for the analyses.

Full Analysis Set (FAS): The FAS includes all enrolled subjects who received at least 1 dose of study drug of CREON-SPL. The FAS will be used for the summary of subject disposition, demographics, and Baseline characteristics.

Per-Protocol (PP) Population: The PP Population includes all enrolled subjects who received at least 1 dose of study drug of CREON-SPL, had Day 1 (Baseline) PEI-Q scores collected, and had at least one post-Baseline PEI-Q scores collected during the Treatment Period (Days 8, 15, 29, and 85). The pharmacodynamic endpoints will be analyzed in the PP Population.

[figure not shown]
Safety Analysis Set for CREON-ABT (SAS-CREON-ABT): The SAS-CREON-ABT consists of all subjects who received at least 1 dose of **CREON-ABT** study drug during the Run-in Period.

Safety Analysis Set for CREON-SPL (SAS-CREON-SPL): The SAS-CREON-SPL consists of all subjects who received at least 1 dose of **CREON-SPL** study drug during the Treatment Period.

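### SAP 9.3 rules out missing PEI-Q data too broadly, and the visit-wise observed-case change at Day 85 has no supporting analysis if subjects who worsen are missing

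*SAP*

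**What the plan says.** SAP 9.3, the section on missing PEI-Q data, opens with "The PEI-Q data are designed to be collected when all questions are answered, so there will be no missing data". It then gives the rule for a missed visit, which SAP 8.0 words identically: "Subjects who have missing PEI-Q data for a particular visit (besides Day 1) will be excluded from the analysis of that visit". Protocol 7.3 agrees: "Subjects who have missing PEI-Q data for the visit will be excluded from the analysis of that visit".

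Missed visits are foreseeable in the same plan. SAP 2.4 reads "Assuming a dropout rate of 20% after the RIV, the number of evaluable subjects will be around 24". SAP 4.0 admits to PP any subject with a CREON-SPL dose, a Day 1 score and one later score, so a subject seen only at Day 8 is in PP but absent from Day 85.

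SAP 9.4.2 reports the mean change from Baseline at each visit with a t-based 95% interval, as Protocol 7.4 does. No model, imputation or missing-data sensitivity analysis is planned. The one sensitivity analysis leaves out a subject who may have been unblinded.

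Protocol 5.8 keeps subjects who stop study drug in all scheduled visits and asks those who withdraw to complete a Premature Discontinuation (PD) Visit. The activity schedule (Protocol Appendix D) ticks the PEI-Q in a column shared by Day 85 and the PD Visit. The SAP does not say to which visit a PD score belongs.

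**The concern.** Forced completion on the ePRO device prevents missing items, not missing questionnaires. A mean over those present is unbiased only if absence is unrelated to the change in symptoms, and the SAP gives no reason to expect that. The study moves clinically controlled subjects to a new API source, and a higher score is worse. If those who worsen tend to be the ones absent, the Day 85 result moves towards no change, which is the reassuring direction. The longest gap between treatment visits, 85 − 29 = 56 days, comes just before Day 85. The observed-case rule leaves the Day 8, 15 and 29 scores of absent subjects out of the Day 85 estimate, although they carry information about it.

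**Working it through.** **The plan's own figures (SAP 2.4, Protocol 7.7).** Inputs: SD 0.7 at one visit, covariance 0.365, 24 evaluable of 30 enrolled.
- Correlation = 0.365 / 0.7² = 0.745.
- SD of change = √(2 × 0.49 − 2 × 0.365) = √0.25 = 0.5.
- Half-length at n = 24 = 1.96 × 0.5 / √24 = 0.200 (normal), or 0.211 (t with 23 df). Both round to the stated 0.2.
- 30 × 0.8 = 24.

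The design figures reproduce.

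**Size of the understatement.** The documents give neither the amount of loss within PP nor its cause, so these are assumptions: 24 subjects, five visits, SD 0.7, equal correlation 0.745; 15% of subjects worsen by 1.0, so the true mean change is 0.15 × 1.0 = 0.15; about 15% are missing at Day 85, with log-odds rising by 1, 2 or 3 per unit of change. The observed-case mean is compared with a likelihood-type estimate: Day 85 is regressed on Days 1 to 29 in those present, and the fit is applied to everyone.

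| Loss depends on | Worsening starts | Observed-case mean (slopes 1, 2, 3) | Estimate using earlier scores |
|---|---|---|---|
| recorded Day 29 change | before Day 29 | 0.11, 0.075, 0.056 | 0.148, 0.144, 0.144 |
| unrecorded Day 85 change | before Day 29 | 0.096, 0.045, 0.017 | 0.128, 0.103, 0.087 |
| unrecorded Day 85 change | after Day 29 | 0.09, 0.05, 0.02 | 0.11, 0.07, 0.04 |

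Understatement = 0.15 − observed-case mean. Share removed = (model − observed) / (0.15 − observed).
- Row 1: understated by 0.04, 0.075, 0.094. Removed: 0.038/0.04 = 95%, 0.069/0.075 = 92%, 0.088/0.094 = 94%.
- Row 2: understated by 0.054, 0.105, 0.133. Removed: 0.032/0.054 = 59%, 0.058/0.105 = 55%, 0.070/0.133 = 53%.
- Row 3: understated by 0.06, 0.10, 0.13. About 20% is removed (for slope 2, 0.02/0.10).

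With 8% missing instead of 15%, the row 1 mechanism gives observed-case means of 0.125, 0.106 and 0.094, an understatement of 0.025, 0.044 and 0.056. Across the scenarios the range is therefore about 0.02 to 0.13.

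**Precision.** In row 1 the SD of the model estimate is 0.133 to 0.136, against 0.123 to 0.133 for observed cases. Root-mean-square error is 0.133, 0.135 and 0.137 against 0.139, 0.148 and 0.159.

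**A harsher mechanism.** Here the true change is 0 and the worst 10 or 20% of changes are removed outright.
- Loss set by the Day 29 change: bias is 0.05 to 0.09 with equal correlation and 0.08 to 0.23 with correlation that decays over visits. Essentially all of it is removed.
- Loss set by the Day 85 change: bias is 0.10 to 0.18 with equal correlation and up to 0.29 with decay. Only 27 to 31% and 55 to 66% is removed, respectively.

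**The case against.** Several points on the other side stand.

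- A reader might infer that the SAP denies missed visits. It does not: the first sentence of 9.3 is best read as being about unanswered questions, and the second deals with absent questionnaires. What remains is one over-broad clause and an untested analysis rule.
- A reader might infer that the earlier scores would correct most of any bias. That holds only when loss depends on scores already recorded. If the worsening first appears in the 56 days before Day 85, only about a fifth is recovered.
- No document supports 15% missing within PP. The 20% runs from the Run-in Visit, so it includes run-in losses and subjects who fail the continuation criteria, and it is already deducted to reach 24. Losing a further 15% leaves 24 × 0.85 = 20.4 of 30, a 32% loss overall. Hence the 8% case.
- Protocol 5.8 is a real safeguard, and some subjects who leave will have a PD score. It does not settle the analysis while that score has no assigned visit.
- Day 8, 15 and 29 changes are each reported, and discontinuation reasons and EPI-type adverse events would also show symptomatic leavers. These make the problem visible but do not alter the Day 85 estimate.
- The study is descriptive, and Protocol 7.4 specifies the t-based interval. An unstructured five-visit covariance has 5 × 6 / 2 = 15 parameters for about 24 subjects. This argues for adding a model, not for replacing the table.

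**Conclusion.** The concern holds in a limited form. The no-missing-data sentence is too broad, and the Day 85 change rests on an observed-case mean with nothing beside it to show sensitivity to loss. If subjects who worsen are the ones missing, the change is understated by about 0.02 to 0.13 in the main scenarios, at most about two thirds of the planned half-length (0.133 / 0.2 = 0.67). The harsher cut-off loss gives more. A model using earlier scores removes nearly all of this, or only about 20 to 60%, depending on whether loss follows recorded or unrecorded change. It gave less bias than the observed-case mean in every scenario run.

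The result rests on assumptions outside the documents: who leaves, how many within PP, when worsening begins, and the correlation between visits. If absence is unrelated to symptoms, there is no bias. The documents do not support a reading that the planned estimate is known to be biased, or that type I error is affected, since nothing is tested. The issue is possible bias in a reported estimate and its interval.

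**What to change.** In the SAP:
1. Limit the no-missing-data sentence in 9.3 to items within a completed questionnaire.
2. Keep the observed-case table and t-based interval that the protocol specifies.
3. Add for TSS, ASDS and BMSS a supportive repeated-measures model on all PP subjects: Days 1, 8, 15, 29 and 85 as a visit factor, one pre-specified covariance structure with a stated fallback, and contrasts of each visit with Day 1.
4. At each visit, print the number missing and their last observed change.
5. State to which visit a PD Visit PEI-Q score belongs.
6. Add a simple check for non-ignorable loss: for example, add fixed amounts to the model-predicted Day 85 scores of absent subjects and report the mean change over that range. With 3 of 24 absent, adding 1.0 moves the mean by 3 × 1.0 / 24 = 0.125.

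The cost is SAP wording, one extra model per score and a short check, with no new data and no departure from the protocol's analysis. The downside is that the model assumes missing at random given earlier scores, and its covariance may be unstable with about 24 subjects. Items 4 and 6 are there because that assumption may fail.

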9.4 Pharmacodynamic Endpoints and Analyses

9.4.1 Pharmacodynamic Endpoints

The pharmacodynamic endpoints include the TSS, ASDS and BMSS at Baseline (Day 1), each of the post-Baseline visits (Day 8, 15, 29 and 85) and change from Baseline to each of the post-Baseline visits.

10.0 Safety Analyses

10.1 General Considerations

Safety data will be summarized for the SAS-CREON-ABT and SAS-CREON-SPL population separately. Safety summaries will be presented by treatment periods using the respective population groups.

10.2 Adverse Events

Per the study protocol, all AEs (non-serious and serious) reported from the time of study drug administration until 30 days post discontinuation of study drug administration will be

collected. In addition, AEs related to study procedures (non-serious and serious) will be collected from the time the subject signed the study-specific informed consent.

All Adverse events (AEs) and Serious Adverse events (SAEs) will be summarized and presented using primary MedDRA System Organ Classes (SOCs) and preferred terms (PTs) coded according to the version of the MedDRA coding dictionary used for the study at the time of database lock. The actual version of the MedDRA coding dictionary used will be noted in the AE tables and in the clinical study report. Specific adverse events will be counted once for each subject for calculating percentages, unless stated otherwise. In addition, if the same adverse event occurs multiple times within a subject, the highest severity and level of relationship to investigational product will be reported.

10.2.1 Treatment-Emergent Adverse Events

Treatment-emergent AEs (TEAE) for the SAS-CREON-ABT are defined as any AE with the onset date on or after the first dose of the CREON-ABT until 30 days after the last dose of CREON-ABT or until the initiation of CREON-SPL, whichever is earlier. Similarly, TEAEs for SAS-CREON-SPL are defined as any AE with the onset date on or after the first dose of CREON-SPL until 30 days after the last dose of CREON-SPL. In the cases that an AE happens in a day that a subject takes both CREON-ABT and CREON-SPL, such AE will be counted under CREON-SPL. This definition will be used for all summaries except the one additional AE overview summaries in Section 10.2.2. If an incomplete onset date was collected for an AE, the AE will be assumed to be treatment-emergent unless there is evidence that confirms that the AE was not treatment-emergent (e.g., the AE end date was prior to the date of the first dose of study drug).

All TEAEs will be summarized overall, as well as by primary MedDRA SOC and Preferred Term. The SOCs will be presented in alphabetical order, and the PTs will be presented in alphabetical order within each SOC.

The number and percentage of subjects experiencing TEAEs will be summarized.

10.2.2 Adverse Event Overview

An overview of AEs will be presented consisting of the number and percentage of subjects experiencing at least one event for each of the following AE categories for the SAS-CREON-ABT and SAS-CREON-SPL:

[figure not shown]
- Any TEAE
- TEAEs with a "reasonable possibility" of being related to study drug according to the investigator
- Severe TEAEs
- Serious TEAEs
- Serious TEAEs with a "reasonable possibility" of being related to study drug according to the investigator
- TEAEs leading to discontinuation of study drug
- TEAEs leading to death
- TEAEs of Special Interest
- TEAEs of Special Interest with a "reasonable possibility" of being related to study drug according to the investigator
- All deaths

The same summaries will be repeated by restricting the analysis period of SAS-CREON-ABT and SAS-CREON-SPL to 28 days after the first dose of CREON-ABT and CREON-SPL, respectively. For SAS-CREON-ABT, the analysis period will not include days on or after the first dose of SAS-CREON-SPL.

The same summaries will also be repeated by using AE rates per 100 patient years of exposure, instead of number and percentage of AEs. For this summary, the definitions of SAS-CREON-ABT and SAS-CREON-SPL in Section 10.2.1 will apply.

